8 ANALYSIS SETS

The following analysis sets will be defined in this study: All Subjects Set, Safety Set in the Ivacaftor Run-in Period, Active Comparator Subjects Set, Full Analysis Set (FAS) in the Active Comparator Treatment Period, and Safety Set in the Active Comparator Treatment Period.

The study has two scheduled dosing period:

Ivacaftor Run-in Period starts from the first dose date of open-label ivacaftor monotherapy and ends prior to randomization.

Active Comparator Treatment Period starts after the randomization to either VX-661/Ivacaftor combination therapy or ivacaftor monotherapy and runs from the first dose date of the randomized study drug during the Active Comparator Treatment Period, to the scheduled last dose at the Week 8 visit.

8.1 All Subjects Set

The **All Subjects Set** is defined as all subjects who were enrolled in either the Ivacaftor Run-in Period or the Active Comparator Treatment Period (i.e., all subjects in the study). This analysis set will be used for all individual subject data listings and for the disposition summary table, unless specified otherwise.

The **Active Comparator Subjects Set** includes all subjects randomized or who received at least 1 dose of study drug in the Active Comparator Treatment Period. This analysis set will be used for specific disposition for the Active Comparator Treatment Period and subject listings related to the Active Comparator Treatment Period only.

8.2 Full Analysis Set

The **Full Analysis Set (FAS)** is defined as all randomized subjects who carry the intended CFTR allele mutation and have received at least 1 dose of study drug during the Active Comparator Treatment Period after randomization. Efficacy analyses will be performed in the FAS in the Active Comparator Treatment Period in which subjects will be analyzed according to their randomized treatment group.

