## 12.2 Analysis Sets

Assignment of subjects to analysis sets will be done before the clinical data lock for the study.

The All Subjects Set is defined as all subjects who were enrolled, randomized, or received at least 1 dose of study drug in either the Ivacaftor Run-in Period or the Active Comparator Treatment Period (i.e., all subjects in the study). This analysis set will be used in subject listings and disposition summary table unless otherwise specified.

The Active Comparator Subjects Set includes all subjects randomized in the Active Comparator Treatment Period or dosed with at least 1 dose of blinded study drug. This analysis set will be used for specific disposition for the Active Comparator Treatment Period and subject listings related to the Active Comparator Treatment Period only.

The Full Analysis Set (FAS) is defined as all randomized subjects who have received at least 1 dose of blinded study drug during the Active Comparator Treatment Period. The FAS is to be used in efficacy analyses in which subjects will be analyzed according to their randomized treatment group.

The Safety Set, defined separately for the Ivacaftor Run-in Period and the Active Comparator Treatment Period, includes all subjects who received at least 1 dose of study drug in the corresponding treatment period. The Safety Set is to be used for all safety analyses in which subjects will be analyzed according to the treatment they received.

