### 12.3.2.1 Subject Disposition

Number and percentage of subjects in the following categories will be summarized separately for the Ivacaftor Run-in Period and the Active Comparator Treatment Period, as appropriate:

- All Subjects Sets
- Dosed (Safety Set) in the Ivacaftor Run-in Period
- Completed treatment in the Ivacaftor Run-in Period
- Prematurely discontinued the treatment during the Ivacaftor Run-in Period and the reasons for treatment discontinuation
- Prematurely discontinued the study during the Ivacaftor Run-in Period and the reasons for study discontinuation
- Active Comparator Subjects Set (Randomized or dosed) in the Active Comparator Treatment Period
- Randomized in the Active Comparator Treatment Period
- Dosed (Safety Set) in the Active Comparator Treatment Period
- Randomized and dosed (FAS) in the Active Comparator Treatment Period
- Completed treatment in the Active Comparator Treatment Period
- Prematurely discontinued the treatment during the Active Comparator Treatment Period and the reasons for treatment discontinuation
- Prematurely discontinued the study during the Active Comparator Treatment Period and the reasons for study discontinuation
- Completed study/Safety Follow-up Visit
- Prematurely discontinued the study after the Active Comparator Treatment Period and the reasons for study discontinuation
- Rollover to extension study

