9.2 Background Characteristics

9.2.1 Subject Disposition

The number and percentage of subjects in the following categories will be summarized:

- All Subjects Set (Number only)

Ivacaftor Run-in Period:

- Dosed (Safety Set) in the Ivacaftor Run-in Period
- Completed treatment in the Ivacaftor Run-in Period
- Prematurely discontinued treatment during the Ivacaftor Run-in period and the reasons for treatment discontinuation

Active Comparator Treatment Period:

- Randomized in the Active Comparator Treatment Period (Number only)

- Dosed in the Active Comparator Treatment Period (Number only)
- FAS (randomized, dosed, and with the intended CFTR allele mutation in the Active Comparator Treatment Period; Number only)
- Completed treatment in the Active Comparator Treatment Period
- Prematurely discontinued treatment during the Active Comparator Treatment Period and the reasons for treatment discontinuation
- Completed the study or the Safety Follow-up Visit
- Prematurely discontinued the study, and the reasons for discontinuation, by the following subcategories:
 - Discontinued the study during the Active Comparator Treatment Period
 - Discontinued the study after the Active Comparator Treatment Period
- Last scheduled visit completed for everyone in FAS

For categories related to the Ivacaftor Run-in Period, the number and percentage of subjects in each disposition category will be summarized, with the number in the safety set in the Ivacaftor Run-in Period as the denominator, together with the number of subjects enrolled but never dosed. A listing will be provided for subjects who discontinued treatment during the Ivacaftor Run-in Period or who discontinued the study during the Ivacaftor Run-in Period with the reasons for discontinuation.

The number and percentage of enrolled subjects in the Ivacaftor Run-in Period will be summarized overall using the number of subjects in the All Subjects Set as the denominator. An enrollment listing will be provided, with subjects enrolled ordered by the enrollment date.

For the categories related to the Active Comparator Treatment Period, the number and percentage of subjects in each disposition category will be summarized, with the number of subjects in the FAS as the denominator, except as noted above.

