The number and percentage of randomized subjects in the Active Comparator Treatment Period will be summarized by stratification factors, and by country and by site, using the Active Comparator Subjects Set. A randomization listing will be provided with subjects ordered by randomization date.

A listing will be provided for subjects who discontinued treatment during the Active Comparator Treatment Period or who discontinued study during the Active Comparator Treatment period with the reasons for discontinuation.

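### Does a genotype-restricted FAS as the disposition denominator leave dosed subjects unaccounted for?

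*SAP*

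**What the plan says.** Protocol Section 12.2 states: "The Full Analysis Set (FAS) is defined as all randomized subjects who have received at least 1 dose of blinded study drug" in the Active Comparator Treatment Period. The protocol's disposition list (Section 12.3.2.1) carries the matching row, "Randomized and dosed (FAS) in the Active Comparator Treatment Period". Genotype is not mentioned in either place.

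SAP Section 8.2 narrows the set to "all randomized subjects who carry the intended CFTR allele mutation and have received at least 1 dose of study drug". The disposition row in SAP Section 9.2.1 repeats the condition: "FAS (randomized, dosed, and with the intended CFTR allele mutation in the Active Comparator Treatment Period; Number only". The narrowing is therefore deliberate and not a slip in one sentence.

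On denominators, SAP Section 9.2.1 computes the Active Comparator rows "with the number of subjects in the FAS as the denominator, except as noted above" and the run-in rows "with the number in the safety set in the Ivacaftor Run-in Period as the denominator". SAP Section 8.1 says of the Active Comparator Subjects Set (randomized or dosed, no genotype condition): "This analysis set will be used for specific disposition for the Active Comparator Treatment Period". Section 9.2.1 also summarizes randomized subjects "by stratification factors, and by country and by site, using the Active Comparator Subjects Set", and it promises a listing of those who stopped treatment or study in this period, with reasons.

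The Safety Set (SAP Section 8.3) has no genotype condition. Adverse event percentages (Section 9.4.1) and exposure (Section 9.2.5) use it. Compliance (Section 9.2.6) uses the FAS.

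**The concern.** Under the protocol, the FAS and the Active Comparator Safety Set contain the same randomized subjects, so it would not matter which one served as a denominator. Once the SAP adds a genotype condition, the two sets can differ. A randomized, dosed subject without an eligible second-allele mutation would count in the adverse event and exposure tables but not in the denominator for completing or stopping. Section 9.2.1 does not say whether that subject stays in the numerators.

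Disposition is where a reader expects every treated subject to be accounted for, and the number stopping for adverse events is commonly checked against it. The SAP also seems to disagree with itself, because Section 8.1 gives this period's disposition to a wider set. At stake is a clean reconciliation between two descriptive tables. The efficacy comparison is not in question: genotype is fixed before randomization, so excluding subjects on it does not depend on the assigned arm, and protocol Section 12.2 has subjects assigned to analysis sets before data lock.

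**Working it through.** **Who could be affected.** Inclusion criterion 4 (protocol Section 9.1) requires the confirmatory genotype result to be reviewed before enrollment. Mutation type is also a randomization stratum (protocol Section 10.3). An affected subject would have to pass both steps in error. The documents give no count, so *k* below is an assumption.

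**Who is excluded.** SAP Section 8.2 does not define the intended mutation, but Appendix A lists ten eligible second-allele mutations, the same ten as protocol Section 16. An analyst would apply that list.

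**Where an excluded subject still appears.**
- Section 9.2.1 prints the randomized, dosed and FAS counts. Dosed minus FAS gives *k*.
- The discontinuation listing is specific to this period, and SAP Sections 8.1 and 9.1 base such listings on the Active Comparator Subjects Set. An excluded subject who stops is listed with a reason; one who is not listed did not stop.
- SAP Section 9.4.1.4 adds a listing of adverse events leading to discontinuation.

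**Size in the pooled table.** With all 160 planned subjects dosed, the adverse event denominator is 160 and the disposition denominator is 160 − *k*:

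| *k* | Disposition denominator | Dosed subjects outside it |
|---|---|---|
| 1 | 159 | 1/160 = 0.6% |
| 2 | 158 | 2/160 = 1.3% |
| 3 | 157 | 3/160 = 1.9% |
| 5 | 155 | 5/160 = 3.1% |

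**Size in one arm.** Take 80 dosed, *k* = 2 and 8 stopping. The 8 borrows the planned 10% dropout purely as an illustration; in the plan that figure is a power assumption, not a rate of stopping treatment. On the dosed set the rate is 8/80 = 10.0%. On the FAS, with numerator and denominator both restricted:
- neither excluded subject stopped: 8/78 = 10.3%
- one stopped: 7/78 = 9.0%
- both stopped: 6/78 = 7.7%

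**Effect on the primary test.** The plan states at least 80% power for a difference of 3.4 points with SD 7, 160 subjects and 10% dropout. Evaluable subjects per arm are 0.9 × 160 / 2 = 72. The standard error is 7 × √(2/72) = 1.167, and 3.4/1.167 = 2.91. Power is 83.0% by the normal approximation and 82.5% by the noncentral t, so the plan's figure is reproduced. With *k* excluded, n per arm is 0.9 × (160 − *k*)/2:

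| *k* | n per arm | Power (noncentral t) |
|---|---|---|
| 0 | 72.0 | 82.5% |
| 1 | 71.55 | 82.3% |
| 4 | 70.2 | 81.5% |
| 8 | 68.4 | 80.5% |

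Power stays above the stated 80% even at 8 exclusions.

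**The case for a change.** The best case for a change is that listings and counts do not repair a summary percentage. If numerators counted everyone dosed over an FAS denominator, completion could exceed 100%: with 80 completing and *k* = 2, 80/78 = 102.6%. Run-in disposition already uses that period's Safety Set, Section 8.1 points to a wider set, and compliance is on the FAS while exposure, which enters its formula, is on the Safety Set. Putting every row on the dosed set would take a few words.

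Little of this stands.
- Percentages above 100% need a numerator drawn from outside the stated denominator. Section 9.2.1 does not instruct that, and a programmer would not do it.
- The FAS exists only for the Active Comparator Treatment Period, so run-in could not use it. Safety Set for run-in and FAS for the randomized period is the protocol's own pattern for baseline characteristics, medications, exposure and compliance (Sections 12.3.2.2 to 12.3.2.4). Compliance is therefore on the set the protocol names.
- The wording of Section 8.1 can be read as covering the counts by stratum, country and site and the period-specific listings, which do use the wider set.
- Moving to the Safety Set would bring problems of its own. That set is analyzed by treatment received and the FAS by randomized group, so a wrongly treated subject could change columns, and the tension with Section 8.1 would remain.
- Reconciliation with adverse events would still not be assured. SAP Section 9.4.1.1 counts withdrawal of either tablet alone as leading to discontinuation, which the disposition row may not.

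What does stand is that Sections 8.1 and 9.2.1 are loosely worded on the disposition set, and that the available text does not explain the departure from the protocol FAS. SAP Section 3 and parts of 9.3 are absent from the public text, and the protocol supplied cannot be matched to the Version 4.0 that the SAP cites, so an explanation may exist.

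**Conclusion.** No change to the plan follows. The SAP does narrow the FAS and does use it as the disposition denominator, so a dosed subject without an eligible mutation would fall outside those percentages. That subject would still be visible in the difference between the dosed and FAS counts and, after stopping, in the listing with reasons. The primary comparison, the Type I error and the efficacy model are untouched.

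The size depends on *k*, which the documents do not give; review of genotype before enrollment makes zero or very few likely. With *k* = 2 of 80 in one arm and 8 stopping, the reported rate differs from 10.0% by between +0.3 and −2.3 percentage points. With *k* = 0 nothing differs. This conclusion assumes that numerators are kept within the stated denominator, that the intended mutation is read as the Appendix A list, and that the discontinuation listing is produced on the Active Comparator Subjects Set as Sections 8.1 and 9.1 indicate. A competent analyst would do all three from the text as it stands.

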8.3 Safety Set

The **Safety Set**, defined separately for the **Ivacaftor Run-in Period** and the **Active Comparator Treatment Period**, includes all subjects who received at least 1 dose of study drug in the corresponding treatment period. The safety analyses will be performed separately for the Ivacaftor Run-in Period and the Active Comparator Treatment Period; subjects will be analyzed according to the treatment they received.

For the safety analysis, the following analyses period will be defined as below:

- The **pre-treatment period (Ivacaftor Run-in Period only)** is defined as the period after the informed consent/assent date and before the initial dosing of study drug in the Ivacaftor Run-in Period.
- The **Treatment-emergent (TE) Period** will be defined separately for the Ivacaftor Run-in Period and the Active Comparator Treatment Period:
 - The TE Period for the Ivacaftor Run-in Period is defined as the date of the first dose in the Ivacaftor Run-in Period to 1) the last day prior to the first dose of the Active Comparator Treatment Period or 2) either the Safety Follow-up Visit or 28 days (inclusive) after the last dose, whichever is earlier, for subjects who discontinue treatment during the Ivacaftor Run-in Period and are not randomized in the Active Comparator Treatment Period.
 - The TE Period for the Active Comparator Treatment Period is defined as the first dose of the Active Comparator Treatment Period to the Safety Follow-up Visit or 28 days (inclusive) after the last dose, whichever is earlier, in the Active Comparator Treatment Period.

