### 12.3.1 General Considerations

All individual subject data for subjects exposed to study drug will be presented in data listings.

**Continuous variables** will be summarized using the following descriptive summary statistics: the number of subjects (n), mean, SD, median, minimum value (min), and maximum value (max).

**Categorical variables** will be summarized using counts and percentages.

Baseline value, absolute change from baseline, and relative change from baseline will be defined separately for the Ivacaftor Run-in Period and the Active Comparator Treatment Period:

- **Baseline value:**
  - Unless otherwise specified, baseline for the Ivacaftor Run-in Period will be defined as the most recent non-missing measurement (scheduled or unscheduled) collected prior to initial administration of Ivacaftor monotherapy.
  - Unless otherwise specified, the baseline for the Active Comparator Treatment Period will be defined as the most recent non-missing measurement (scheduled or unscheduled) collected prior to initial administration of the VX-661/ivacaftor combination therapy, but no earlier than the measurement at Week -2.
  - For spirometry, the baseline value used for the Active Comparator Treatment Period will be the average of the measurement at Week -2 and the measurement on Day 1 predose. If a subject has an AE leading to an approved extension of the Ivacaftor Run-in Period, and the Week -2 spirometry assessment is between the start and end date (inclusive) of the AE, then the measurement on Day 1 predose will serve as baseline for the Active Comparator Treatment Period.
  - For ECG, the baseline will be defined as the average of the 3 pretreatment measurements at the first day of the corresponding treatment period.
- **Change (absolute change) from baseline** will be calculated as postbaseline value - baseline value.
- **Relative change from baseline** will be calculated as (postbaseline value - baseline value)/baseline value.

The Treatment-emergent (TE) Period will be defined separately for the Ivacaftor Run-in Period and the Active Comparator Treatment Period:

- The TE Period for the Ivacaftor Run-in Period is defined as the first dose in the Ivacaftor Run-in Period to the earlier of the last day prior to the first dose of the Active Comparator Treatment Period or either the Safety Follow-up Visit or 28 days (inclusive) after the last dose for subjects who do not have Safety Follow-up Visit in the Ivacaftor Run-in Period.

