#### **12.3.4.2 Clinical Laboratory Assessments**

The raw values and change from the corresponding treatment period baseline values of the continuous laboratory parameters will be summarized in SI units at each scheduled time point during the TE Period based on the corresponding Safety Set for the Ivacaftor Run-in

Period, and by treatment group for the Active Comparator Treatment Period, separately. In addition, mean value at each visit will be plotted for each of the liver function parameters. The plots will be separate for the Ivacaftor Run-in Period and by treatment groups in the Active Comparator Treatment Period.

The number and percentage of subjects with at least 1 potentially clinically significant (PCS) event during the treatment-emergent period will be summarized for the Ivacaftor Run-in Period and by treatment group during the Active Comparator Treatment Period, separately. The PCS (postbaseline) shift from the corresponding treatment period baseline will also be summarized for selected laboratory parameters for the Ivacaftor Run-in Period and by treatment groups in the Active Comparator Treatment Period, separately, separately. The PCS criteria and the parameter selection criteria will be provided in the SAP.

Results of urinalysis and the serum pregnancy test will be listed in individual subject data listings only. In addition, a listing containing individual subject laboratory assessment values outside the reference ranges will be provided. This listing will include data from scheduled and unscheduled time points.

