9.3.1.2 Summary in Ivacaftor Run-in Period

Percent predicted FEV₁, both the raw values and their absolute change from baseline, will be summarized by visit for the Ivacaftor Run-in Period (Week -4, Week -2 and Day 1 predose).

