9.4.1.5 Clinical Laboratory

The analysis of clinical laboratory measurements will be presented separately for the Ivacaftor Run-in Period and by treatment group at each scheduled time point for the Active Comparator Treatment Period based on the corresponding Safety Set.

For treatment-emergent laboratory measurements, the raw values and change from baseline values of the continuous hematology and chemistry results, including coagulation studies will be summarized in SI units by treatment group and visit.

The number and percentage of subjects with at least 1 potentially clinically significant (PCS) laboratory event during the TE period will be summarized overall and by treatment group, including the shift of the PCS event from baseline to postbaseline. The PCS criteria are provided in [Appendix I](#).

For each liver function test (LFT) laboratory test (alanine aminotransferase [ALT], aspartate aminotransferase [AST], alkaline phosphatase [ALP], gamma-glutamyl transferase [GGT], and total bilirubin), the following additional analyses will be conducted for the Active Comparator Treatment Period:

- A listing of subjects with elevated LFT results during the TE period will be presented. For each subject in the listing, LFT assessments at all time points will be included (scheduled and unscheduled).
- For each of the LFTs, mean values (±SD) will be plotted by visit, and a box plot of the LFT value/ULN will be plotted by visit.
- The incidence of LFTs meeting threshold criteria
- For each of the LFTs, mean values (±SD) will be plotted by visit, and a box plot of the LFT value/ULN will be plotted by visit.
- The incidence of LFTs meeting threshold criteria against the baseline threshold criteria also will be summarized by treatment group, LFT parameters, and visit (only shifts to values worse than baseline will be presented).

- A scatter plot of the maximum ALT value across visits versus the maximum total bilirubin value also will be presented. The ALT and total bilirubin values will be presented on a logarithmic scale. The graph will be divided into 4 quadrants with a vertical line corresponding to 3xULN for ALT and a horizontal line corresponding to 2xULN for total bilirubin. A similar graph of maximum AST value versus maximum total bilirubin value will be presented as well.

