	Baseline for the Ivacaftor Run-in Period (Week -4)	-28	[screening visit, 1 st dose day for the Ivacaftor Run-in Period]
	Week -2	-14	[1 day after 1 st dose day for the Ivacaftor Run-in Period, 1 day prior to 1 st dose day for the Active Comparator Treatment Period]
	Baseline for the Active Comparator Treatment Period	1	[1, 1]
	Week 4	29	[2, 43]
	Week 8	57	[44, 71]
	ETT	N/A	Follow the individual visit window to be mapped to individual visits
	Safety Follow-up Visit [REDACTED]	N/A	Efficacy assessments: follow the individual visit window to be mapped to individual visits if measured before / on Day 71 or remain as SFU if otherwise. Safety assessments: remain as SFU
	Baseline for the Ivacaftor Run-in Period (Week -4)	-28	[screening visit, 1 st dose day for the Ivacaftor Run-in Period]
	Baseline for the Active Comparator Treatment Period	1	[1 day after 1 st dose day for the Ivacaftor Run-in Period, 1]
	Week 4	29	[2, 43]
	Week 8	57	[44, 71]
•Sweat chloride •Hematology [REDACTED]			

	ETT		N/A	Follow the individual visit window to be mapped to individual visits
	Safety Follow-up Visit		N/A	Efficacy assessments: follow the individual visit window to be mapped to individual visits if measured before / on Day 71 or remain as SFU if otherwise. Safety assessments: remain as SFU
	Baseline for the Ivacaftor Run-in Period (Week 4)		-28	[screening visit, 1 st dose day for the Ivacaftor Run-in Period]
	Baseline for the Active Comparator Treatment Period		1	[1 day after 1 st dose day for the Ivacaftor Run-in Period, 1]
	Week 8		57	[2, 71]
	ETT		N/A	Follow the individual visit window to be mapped to individual visits
	Safety Follow-up Visit		N/A	Efficacy assessments: follow the individual visit window to be mapped to individual visits if measured before / on Day 71 or remain as SFU if otherwise. Safety assessments: remain as SFU
	Baseline for the Active Comparator Treatment Period		1	[1, 1]
	Week 8		57	[2, 71]
	ETT		N/A	Follow the individual visit window to be mapped to individual visits
	Safety Follow-up Visit		N/A	Safety assessments: remain as SFU

- Urinalysis
- Coagulation

- Lipid panel

Note:

1. To apply the above visit windows, please first determine the baseline measurements based on the first dose for the Active Comparator Treatment Period and then label Day 1 for the date of the first dose for the Active Comparator Treatment Period. Day 1 will be used to indicate the 1st dose date for the Active Comparator Treatment Period.

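### For subjects who complete the ivacaftor run-in, the run-in treatment-emergent period closes before the Day 1 predose samples, so the run-in safety summaries have no scheduled post-baseline hematology or coagulation value for them

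*SAP*

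**What the plan says.** **End of the run-in TE period.** SAP 8.3 gives two branches. Subjects who go on to randomized dosing fall under the first: "1) the last day prior to the first dose of the Active Comparator Treatment Period or 2". Run-in discontinuers fall under the second, which runs to "either the Safety Follow-up Visit or 28 days (inclusive) after the last dose, whichever is earlier, for subjects who discontinue treatment during the Ivacaftor" period. Protocol 12.3.1 sets the same limit for completers, at "the earlier of the last day prior to the first dose of the Active Comparator Treatment Period".

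**Start of the next TE period.** In SAP 8.3 the Active Comparator TE period "is defined as the first dose of the Active Comparator Treatment Period to the Safety Follow-up Visit" or 28 days after the last dose. It opens with the first randomized dose.

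**Planned run-in laboratory summaries.** Protocol 12.3.4.2 plans values and changes "at each scheduled time point during the TE Period based on the corresponding Safety Set for the Ivacaftor Run-in" Period, together with run-in counts and shifts for potentially clinically significant (PCS) results. SAP 9.4.1.5 presents the laboratory analysis separately for the run-in and specifies: "For treatment-emergent laboratory measurements, the raw values and change from baseline values of the continuous hematology and chemistry results", with coagulation included. SAP 9.1 applies the TE periods to safety analyses unless another rule is stated.

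**Visit windows.** In SAP Appendix D, Table 12-D, the hematology and coagulation window for the Active Comparator baseline reads "1 day after 1 st dose day for the Ivacaftor Run-in Period, 1", so it covers the whole run-in after its first dosing day, up to and including Day 1.

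**A different treatment of lung function.** In SAP 9.3.1.2, percent predicted FEV1 "will be summarized by visit for the Ivacaftor Run-in Period (Week -4, Week -2 and Day 1 predose").

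**The concern.** The run-in safety tables are meant to describe what happens on about 4 weeks of ivacaftor. The one scheduled assessment that shows the full 4 weeks is the Day 1 predose visit, and the TE rule stops one day before it. For panels with no mid-run-in draw, nothing scheduled remains after baseline.

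Two consequences follow. First, a laboratory abnormality first seen at the end of the run-in is not counted as treatment-emergent in the run-in, and it becomes the reference value for the randomized period. For liver tests, SAP 9.4.1.5 shows only shifts to values worse than baseline, so an elevation already present on Day 1 that persists unchanged would not appear in that shift table. Second, the programmer must either depart from the written TE definition or deliver run-in hematology and coagulation tables whose only scheduled post-baseline data come from subjects who stopped early.

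**Working it through.** The plan gives no figure on this point to reproduce. The check is a count of scheduled assessments.

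**Inputs**
- Schedule: protocol Table 3-2, nominal days -28 (Week -4), -14 (Week -2) and 1.
- Timing: blood at Week -4 and Day 1 is drawn before dosing (protocol 11.7.2). Vital signs, pulse oximetry and the baseline ECGs are also taken before dosing (Table 3-2 footnotes).
- Day 1 is the date of the first randomized dose (SAP Appendix D, note 1), so the preceding day is Day -1.
- Baseline rule: the last value before the first dose of each period (SAP 9.1). For ECG it is the mean of the predose triplicate.

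**Classification for a run-in completer**
- Day -28 predose: run-in baseline.
- After Day -28 through Day -1: run-in TE.
- Day 1 predose: after the run-in TE period has ended and before the Active Comparator TE period has begun, so in neither. It is the Active Comparator baseline.

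Values kept = number of scheduled days d with -28 < d ≤ -1. Values available = values kept + 1 for the Day 1 predose assessment.

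| Assessment | Scheduled days through Day 1 | Kept as written | Available if Day 1 predose counts | Lost |
|---|---|---|---|---|
| Hematology | -28, 1 | 0 | 1 | 1 of 1 (100%) |
| Coagulation | -28, 1 | 0 | 1 | 1 of 1 (100%) |
| Serum chemistry, liver tests | -28, -14, 1 | 1 | 2 | 1 of 2 (50%) |
| ECG, vital signs, pulse oximetry | -28, -14, 1 | 1 | 2 | 1 of 2 (50%) |

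For ECG, the run-in summary at issue is the one in protocol 12.3.4.3. The by-visit summary in SAP 9.4.2 names only the active treatment period.

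**Other sources of data.** Run-in discontinuers attend an Early Treatment Termination (ETT) Visit and a Safety Follow-up Visit (protocol 8.1.2), and hematology and coagulation are scheduled at both. Under the second branch of SAP 8.3 these values can fall inside the run-in TE period, although a Safety Follow-up sample (28 ± 7 days) counts only if taken within 28 days of the last dose. Table 12-D has no run-in post-baseline row for hematology or coagulation to which their ETT values could be mapped. Unscheduled run-in draws may count toward PCS results but have no run-in visit either.

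**The case against.** The run-in is an uncontrolled, open-label lead-in on ivacaftor at an approved regimen, and its purpose is to set a baseline. Some subjects will already have been taking ivacaftor before Week -4, so their run-in baseline is not drug-naive. Clinically significant laboratory abnormalities are reported as adverse events in any case (protocol 11.7.2). An abnormality that persists after Day 1 can still count in the Active Comparator PCS incidence. The FEV1 summary is an efficacy summary, and Table 12-D gives Day 1 spirometry the same Active Comparator baseline label, so the label alone does not bar a run-in use.

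All of this limits the harm. It does not remove the gap: FEV1 has an explicit statement that Day 1 predose is a run-in visit, whereas the safety panels have none and fall under the TE rule by default.

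A reader might infer more than the documents support:
- **That Day 1 values go unused.** They are the Active Comparator baseline, enter its change and shift tables, and appear in listings.
- **That the run-in tables hold no scheduled post-baseline data at all.** Discontinuers can contribute, as shown above.
- **That urinalysis is affected.** Both documents only list it.
- **That a known number of PCS cases is missed, or that a reassuring near-zero rate will be reported.** The documents give no PCS rate per draw. They refer to the corresponding Safety Set but do not spell out the denominator for laboratory PCS percentages, as SAP 9.4.1 does for adverse events.

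**Conclusion.** The point holds for subjects who complete the run-in. As written, they have 0 scheduled post-baseline hematology and coagulation values in the run-in summaries, and 1 of 2 for serum chemistry, ECG, vital signs and pulse oximetry. The only scheduled post-baseline hematology and coagulation data that could enter come from run-in discontinuers, who do not represent the run-in population.

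This is a stated rule that defeats a planned table. It is not a conflict between the documents, since protocol and SAP share the cut-off. The efficacy analyses and the randomized safety comparison are untouched. It should be corrected, but it does not threaten the trial's main conclusions. The counts assume the nominal visit schedule and a literal reading of the TE rule; they rest on no assumed event rate.

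**What to change.** 1. In SAP 8.3 and protocol 12.3.1, state that for safety assessments other than adverse events the run-in TE period extends to immediately before the first randomized dose. Day 1 predose is then both the last run-in post-baseline value and the Active Comparator baseline, as SAP 9.3.1.2 already allows for FEV1.
2. In Table 12-D, add a run-in analysis visit, Day 1 predose (end of run-in), for hematology, coagulation, serum chemistry, ECG, vital signs and pulse oximetry.
3. Leave adverse event dating unchanged. Add a footnote that a Day 1 predose laboratory abnormality may appear in the run-in laboratory table while an adverse event with Day 1 onset is assigned to the Active Comparator period.

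The cost is a small wording change in both documents, the extra analysis-visit row and minor programming. No new data are collected. The downside is that one measurement appears in two period-specific tables, and the footnote is needed so that laboratory and adverse event tables are not read as contradictory.
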